9.3.3. Laboratory Tests

All laboratory data will be listed and only central laboratory data will be summarized. Laboratory data and change from baseline (haematology, biochemistry or urinalysis) will be summarized with descriptive statistics (continuous variables) or as distributions (categorical variables) by visit up to week 48 except for pregnancy test parameter. For urinalysis parameter, a shift table from baseline up to Week 48 will be presented.

The categories for out of reference range will be Low, Normal and High for Hematology, Biochemistry, Urinalysis and Coagulation, and Normal and Abnormal for Urinalysis (Qualitative Value). For these categories, a shift table from baseline to each visit up to Week 48 will be presented.

Laboratory test values will be considered potentially clinically significant (PCS) if they meet either the low or high PCSV criteria listed in section 8.4.3.4. A shift table describing the number and percentage of subjects shifting from non PCSV at baseline to PCSV at post-baseline will be performed any time during treatment period.

The percentages will be calculated from the number of subjects with available baseline values and any time post-baseline value

9.3.4. Vital Signs

Vital sign measurements and their change from baseline will be listed and summarized using descriptive statistics by visit up to week 48. Those parameters will include: heart rate (HR), supine and standing blood pressure (BP) (both systolic and diastolic), body temperature and weight. Furthermore, orthostatic vital sign and supine minus standing blood pressure (both systolic and diastolic) and their change from baseline will be summarized with descriptive statistics by visit.

Vital sign values will be considered PCSV if they meet both criteria of the observed value and the change from baseline listed in section 8.4.3.6. The number and percentage of subjects with PCSV at any time post-baseline will be tabulated. The percentages will be calculated from the number of subjects with a baseline value and any time post-baseline value. The number and percentage of subjects with orthostatic hypotension as defined in section 8.4.3.6 will be summarized in the same way.

9.3.5. 12-Lead ECGs

All ECGs parameters will be listed and analyzed.

The ECGs will be assessed by the investigator and deemed “Normal”, “Abnormal, not clinically significant” (Abnormal, NCS) and “Abnormal, clinically significant” (Abnormal, CS) and tabulated by visit up to week 48 using frequency counts and percentages.

In addition, the numerical ECG parameters and their change from baseline generated by the central ECG laboratory (see section 8.4.3.5) will be summarized by descriptive statistics for each parameter by visit.

ECG parameters values will be considered PCSV if they meet the criteria listed in section 8.4.3.5. The number and percentage of subjects with PCSV will be tabulated. The percentages are to be calculated from the number of subjects with available baseline values and any time post-baseline value for a specific category.

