#### **Orthostatic Hypotension**

The number and percentage of "abnormal" by the Investigator in orthostatic hypotension will be summarized at each visit by treatment group.

For evaluation ("Normal/Abnormal") by the Investigator in vital signs, a shift table of the change from baseline will be summarized at each visit by treatment group.

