#### Vital Signs

Vital signs (sitting systolic/diastolic blood pressure, orthostatic hypotension, heart rate, respiratory rate, and axillary, oral, temporal [skin-based], or tympanic body temperature) will be descriptively summarized for values and the changes from baseline at each visit.

For evaluation ("Normal/abnormal CS/abnormal NCS") by the Investigator in vital signs, a shift table of the change from baseline will be summarized at each visit by treatment group.

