8.4.3.6. Vital Signs

The following measurements will be performed: sitting systolic and diastolic blood pressure, heart rate (eg, beats per minute), respiratory rate, and axillary, oral, temporal (skin-based), or tympanic body temperature (eg, Celsius). The Investigator will perform an overall evaluation for safety purposes and the recording will be reported as 'normal', 'abnormal clinically significant (CS)', or 'abnormal not clinically significant (NCS)'.

Criteria of Potentially Clinically Significant Values (PCSV) for Vital⁷

The following criteria to determine risk for PCSV for Vital signs are defined:

HR* at post-baseline ≤ 50 bpm and decrease from baseline ≥ 15 bpm

HR* at post-baseline ≥ 120 bpm and increase from baseline ≥ 15 bpm

SBP at post-baseline ≤ 90 mmHg and decrease from baseline ≥ 20 mmHg

SBP at post-baseline ≥ 180 mmHg and increase from baseline ≥ 20 mmHg

DBP at post-baseline ≤ 50 mmHg and decrease from baseline ≥ 15 mmHg

DBP at post-baseline ≥ 105 mmHg and increase from baseline ≥ 15 mmHg

Note: *HR will be regarded as Pulse Rate.

Orthostatic Hypotension

Orthostatic hypotension will be defined as experiencing lightheadedness and/or dizziness and/or a reduction in systolic BP of 20 mmHg or more, and/or a reduction in diastolic BP of 10 mmHg or more, or increase in heart rate > 20 beats/minute for the standing measurement compared to the supine measurement.

The following criteria to determine "Orthostatic vital sign changes" are defined:

- Decrease of ≥ 20 mmHg from 'Seated (resting 5 minutes)' Systolic Blood pressure to 'Standing (after 1 minute)' Systolic Blood pressure
- Decrease of ≥ 20 mmHg from 'Seated (resting 5 minutes)' Systolic Blood pressure to 'Standing (after 3 minutes)' Systolic Blood pressure
- Decrease of ≥ 10 mmHg from 'Seated (resting 5 minutes)' Diastolic Blood pressure to 'Standing (after 1 minute)' Diastolic Blood pressure
- Decrease of ≥ 10 mmHg from 'Seated (resting 5 minutes)' Diastolic Blood pressure to 'Standing (after 3 minutes)' Diastolic Blood pressure
- Increase of > 20 bpm from 'Seated (resting 5 minutes)' Pulse rate to 'Standing (after 1 minute)' Pulse rate

- Increase of >20 bpm from 'Seated (resting 5 minutes)' Pulse rate to 'Standing (after 3 minutes)' Pulse rate

The Investigator will also evaluate any clinical symptoms due to the orthostatic vital sign changes such as dizziness and lightheadness.

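### The SAP's orthostatic hypotension count pools new cases with cases already present at baseline, and the protocol's by-visit and shift tables that would help separate them are omitted without being declared

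*SAP*

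**What the plan says.** **Count.** For vital signs with potentially clinically significant values (PCSV), SAP 9.3.4 says: "The number and percentage of subjects with PCSV at any time post-baseline will be tabulated". The denominator follows: "The percentages will be calculated from the number of subjects with a baseline value and any time post-baseline value". The same paragraph then extends this to orthostatic hypotension: "The number and percentage of subjects with orthostatic hypotension as defined in section 8.4.3.6 will be summarized in the same way".

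**Definitions.** A vital-sign value qualifies as PCSV only "if they meet both criteria of the observed value and the change from baseline listed in section 8.4.3.6". The orthostatic definition in SAP 8.4.3.6 begins: "Orthostatic hypotension will be defined as experiencing lightheadedness and/or dizziness and/or a reduction in systolic BP of 20 mmHg or more". It continues with a diastolic fall or a heart-rate rise on standing. None of its terms refers to the study baseline.

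**Protocol tables.** Under Orthostatic Hypotension, Protocol 17.4.5.9 plans the number and percentage with an abnormal investigator result at each visit by arm. For a Normal/Abnormal evaluation it also plans "a shift table of the change from baseline will be summarized at each visit by treatment group". Under Vital Signs it plans a second shift table, for the three-category evaluation (normal, abnormal CS, abnormal NCS) "by the Investigator in vital signs, a shift table of the change from baseline will be summarized at each visit by treatment group".

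**What the SAP carries forward.** SAP 9.3.4 contains none of these three tables. SAP Section 11 lists two changes from the protocol, the physical-examination summary and the FAS definition, and neither concerns orthostatic hypotension or vital signs.

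**The concern.** Orthostatic hypotension is a named safety endpoint in both documents, and the secondary objective is to compare the safety of the two regimens. A reader of the safety tables will want to know how many subjects developed the condition on each regimen. The planned count does not answer that, because the denominator requires a baseline value but the rule makes no use of baseline status.

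The any-time-post-baseline rule suits the vital-sign PCSVs, which have a change from baseline built in. Applied to a definition without that element, it counts everyone positive after baseline, whether or not they were positive before dosing. Cases common to both arms then dilute the contrast between regimens. The protocol's shift table would have shown who moved from Normal to Abnormal. Without it, no categorical output under SAP 9.3.4 shows this for orthostatic hypotension.

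**Working it through.** **Step 1: text comparison.** How the SAP treats baseline in its categorical safety outputs:

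| Output | Baseline used? |
|---|---|
| Vital-sign PCSV (8.4.3.6, 9.3.4) | Yes: change from baseline is part of the criterion |
| Laboratory PCSV (9.3.3) | Yes, in the numerator: "A shift table describing the number and percentage of subjects shifting from non PCSV at baseline to PCSV at post-baseline" |
| ECG QRS and QTc criteria (8.4.3.5) | Yes: value at or below the limit at baseline, or a change from baseline |
| Numbness and unsteadiness (9.3.1.1) | Yes: shift table |
| Orthostatic hypotension (8.4.3.6, 9.3.4) | No |

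The baseline data exist. Table 1 schedules vital signs at screening and Day 1, and its footnote includes orthostatic hypotension among them. Vital signs are repeated at Weeks 4, 8, 12, 24, 36 and 48, which gives six post-baseline visits at which a baseline case can qualify again.

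**Step 2: what the count estimates.** The documents state no figure on this point, so there is none to reproduce. Let

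- b = baseline prevalence, the same in both arms in expectation because of randomization;
- p_i = new-onset proportion in arm i among subjects free of the condition at baseline;
- r_i = proportion of baseline cases in arm i that are positive again after baseline.

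The SAP count in arm i is q_i = b·r_i + (1 − b)·p_i.

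The difference is q_1 − q_2 = (1 − b)(p_1 − p_2) + b(r_1 − r_2).

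With equal recurrence (r_1 = r_2 = r) this becomes (1 − b)(p_1 − p_2). The absolute difference shrinks by the factor (1 − b) whatever r is. The ratio moves toward 1 when r > 0, because b·r is added to both arms.

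**Step 3: illustration.** The documents give none of b, p_1, p_2 or r. The values below are assumptions, shown as a range. Worked row, b = 10% and r = 1: 0.10 + 0.90 × 0.20 = 28%, against 0.10 + 0.90 × 0.10 = 19%; difference 9 points; ratio 28/19 = 1.47.

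Assumed new onset 20% versus 10% (true difference 10 points, ratio 2.00):

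| b | SAP count, r = 1 | Difference (any r) | Ratio, r = 1 | Ratio, r = 0.5 |
|---|---|---|---|---|
| 0% | 20% vs 10% | 10.0 | 2.00 | 2.00 |
| 5% | 24.0% vs 14.5% | 9.5 | 1.66 | 1.79 |
| 10% | 28% vs 19% | 9.0 | 1.47 | 1.64 |
| 20% | 36% vs 28% | 8.0 | 1.29 | 1.44 |
| 30% | 44% vs 37% | 7.0 | 1.19 | 1.32 |

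Assumed new onset 15% versus 8% (true difference 7 points, ratio 1.88):

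| b | Difference (any r) | Ratio, r = 1 | Ratio, r = 0.5 |
|---|---|---|---|
| 5% | 6.65 | 1.53 | 1.66 |
| 10% | 6.3 | 1.37 | 1.52 |
| 20% | 5.6 | 1.21 | 1.34 |
| 30% | 4.9 | 1.14 | 1.24 |

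Counting new cases among baseline-free subjects returns the true difference and ratio at every b.

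**The case against.** **The count is valid for what it is.** A subject positive only at baseline is not counted, and one positive after baseline does have the condition on treatment. The SAP nowhere calls the figure incidence or new onset. This stands: the table is a correct total that lacks a companion. A reader might infer that the SAP misreports incidence, but the text makes no such claim.

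**No test is weakened.** One could turn Step 3 into power. With 20% versus 10%, full recurrence and b = 10%, a nominal 5% comparison would have 54% power on the SAP count (190 per arm), against 74% on new onset (171 baseline-free per arm). No between-regimen test of orthostatic hypotension is planned, so these figures are illustrative only. Nor is one regimen favoured: randomization balances baseline cases in expectation.

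**The SAP uses baseline elsewhere.** SAP 9.3.4 summarizes continuous orthostatic values and their change from baseline by visit. Clinically significant vital-sign abnormalities are reported as AEs (Protocol 13.2), and TEAEs must start or worsen after dosing. Both are partial answers. Means do not show who became abnormal, and the AE route depends on a judgement of clinical significance, not on the SAP's criteria.

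**The laboratory rule is not an exact precedent.** It restricts the numerator to shifts from non-PCSV, but its denominator is the same as in 9.3.4. This is correct. It shows that baseline is used, not that a baseline-free denominator is already house style.

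**The protocol tables may still stand.** SAP Section 2 gives the SAP precedence for details it describes, and on these tables it is silent. The protocol's two-category shift sentence also names vital signs, although its heading and scale point to orthostatic hypotension. So the documents do not show a decision to abolish the tables. Yet Section 11 declares the dropped physical-examination summary, so a reader would expect these omissions there too.

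**The hypersensitivity warning.** Protocol 8.2.1 mentions decreased blood pressure within anaphylaxis reports for IV edaravone. Those are acute reactions, not postural changes at scheduled visits, and the point does not rely on them.

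**Replacing the count would lose information.** If one regimen makes baseline cases more likely to recur (r_1 ≠ r_2), the total count carries that signal and a new-onset count does not. This stands and shapes the fix.

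**Conclusion.** The point holds as a gap in a descriptive safety analysis. The SAP's rule pools baseline cases that recur with new cases, because the orthostatic definition, unlike the vital-sign PCSVs, has no baseline element. Three tables planned in Protocol 17.4.5.9 are absent from the SAP, and Section 11 does not say so.

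The size cannot be determined from the documents. Under equal recurrence, the absolute difference is reduced by the share of subjects positive at baseline: 5% of its value at b = 5%, 20% at b = 20%, nothing at b = 0. The ratio is more sensitive: under the 20% versus 10% assumption with full recurrence it falls from 2.00 to 1.47 at b = 10%. The textual finding does not depend on these assumptions; the numbers depend on them entirely. It is worth correcting because the endpoint is named, the data are already collected and the protocol had already planned the tables.

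**What to change.** In SAP 9.3.4:

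1. Keep the any-time-post-baseline count and label it as total on-treatment orthostatic hypotension.
2. Add the number and percentage of subjects with new orthostatic hypotension at any time post-baseline, among those without it at baseline, by treatment group.
3. Restore the Protocol 17.4.5.9 tables by treatment group: investigator orthostatic Abnormal by visit, its Normal/Abnormal shift from baseline, and the three-category vital-sign shift. Alternatively, declare and justify their removal in Section 11.

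A new-onset flag also needs one definition. The definition in SAP 8.4.3.6 compares standing with supine, while its criteria list uses seated. The heart-rate threshold is strictly above 20 beats/minute in the SAP but at or above 20 in Protocol 13.3. These passages must be reconciled.

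The cost is SAP wording and a few standard tables from data already collected. The new-onset denominator is slightly smaller (171 instead of 190 per arm at an assumed 10% prevalence, 190 × 0.90).

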9.3.6. Physical Examinations

Physical examination will be listed.

9.4. Subgroup analysis

The following subgroups will be analyzed for the key and the other secondary endpoints. For the continuous endpoints using MMRM (Change of %SVC, ALSAQ40 total score and ALSFRS-R total score), the model specified in section 9.2.1.1 will include additional fixed factor for the subgroup variable, the subgroup by treatment interaction as well as the subgroup by treatment by visit interaction. The influence of each subgroup factor will be investigated using the p-values for the interaction terms.

For the time to death, tracheostomy, or permanent assisted mechanical ventilation then the same Cox proportional hazard regression model will be used while adding the subgroup variable as well as the subgroup by treatment interaction. The influence of each subgroup factor will be investigated using the p-values for the interaction terms.

In addition, forest plot depicting the treatment effect and 95% CI for all subgroups will be displayed for change of ALSFRS-R total score and the time to death, tracheostomy, or permanent assisted mechanical ventilation.

Note: In some subgroup analyses, some factor will be statistically adjusted (e.g., in the country subgroup analysis, the Region factor will be removed).

- Gender (Female; Male)
- Race (White; Black; Asian; Other)
- Age (≥ 65 years old; < 65 years old)
- Region (North America; Europe; Asia)
- Body Weight (\geq Median; $<$ Median)
- BMI (\geq Median; $<$ Median)
- Country (United States; Canada; Germany; Italy; Switzerland; Japan; South Korea)
- Ethnicity (Hispanic or Latino; Other)
- Disease duration from onset of symptoms (< 1 year; ≥ 1 year)
- Disease duration from onset of diagnosis (< 1 year; ≥ 1 year)
- ALSFRS-R score at baseline (\geq Median; $<$ Median)
- ALSFRS deterioration strata for randomization (-1, -2; -3, -4)
- Initial symptom (Bulbar; Limb)
- ALS diagnosis (Sporadic; Familial)
- El Escorial revised Airlie House Diagnostic Criteria (Definite; Probable ALS)
- Concomitant use of riluzole (Present; Absent)
- Concomitant use of AMX0035 (Present; Absent)
- %FVC at baseline ($\geq 80\%$; $< 80\%$)
- %SVC at baseline ($\geq 80\%$; $< 80\%$)

- [REDACTED] at baseline (\geq Median; $<$ Median)
- [REDACTED] at baseline (\geq Median; $<$ Median)
- [REDACTED] at baseline (\geq Median; $<$ Median)
- [REDACTED] at baseline (\geq Median; $<$ Median)

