- In case the event is not observed until the last observed visit date when week 48 data base is locked, a right censoring will be performed for each subject at the last observed date of treatment. the time variable for each subjects will be calculated as:
 - Last observed Date - Randomization date +1
- Indicator (censoring) variable will be created to indicate an event (0) if the event was observed or censoring (1) if the event is not observed and at week 48 data base lock the subjects was either discontinued or is ongoing.
-

8.4.2.5. Time to death or permanent assisted mechanical ventilation:

Variable derivation will be performed similar to the time to death, tracheostomy, or permanent assisted mechanical ventilation.

8.4.2.6. Time to death:

Variable derivation will be performed similar to the time to death, tracheostomy, or permanent assisted mechanical ventilation.

8.4.2.7. Changes from baseline in ALSFRS-R score at Weeks 4, 8, 12, 24, 36, and 48

ALSFRS-R is a questionnaire used to measure the impact of ALS that is evaluated by the Investigator. The scale measures the subjects' physical function across 12 activities of daily living. The date of the evaluation along with the results will be recoded on the eCRF with respect to "4 Handwriting" and "5 eating motion," the results for the dominant hand (the hand used in daily life at the time of screening) will be recorded.

- ALSFRS-R total score for each visit will be derived from the sum of 12 items²
For the item 5 “Eating disorder,” either the item (a) or (b) will be selected corresponding to subjects with or without gastrostomy respectively. The maximum total score is $4 \times 12 = 48$.
- ALSFRS-R domains Score. The following subdomain will be calculated for each visit as well as the change from baseline to week 48.
 - Bulbar function = total of items 1 to 3
 - Limb function = total of items 4 to 9
 - Fine motor function = total of items 4 to 6
 - Gross motor function = total of items 7 to 9
 - Respiratory function = total of items 10 to 12

8.4.2.7.1. Change from screening and baseline in %Forced Vital Capacity (%FVC) at Week 24 and 48

FVC measurements will be conducted in clinic at around the same time of day where possible with the subject in sitting upright position. Subjects should make at least 3 attempts to generate acceptable and reproducible FVC data. The best value will be selected and will be recorded in the eCRF.

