9.2.1.1. Primary Analysis

More than a few death events ($\geq 5\%$ death percentage for all randomized subjects, eg, ≥ 19 death events) were observed in the data review meeting, the primary endpoint analysis using mixed model repeated measures (MMRM) was replaced with the ranking score on CAFS score at Week 48 based on a joint rank score derived from change from baseline in ALSFRS-R score and time to death through Week 48 with analysis of covariance (ANCOVA) specified in the secondary endpoint analysis. Therefore, the primary analysis will be the CAFS analysis at week 48 using ANCOVA following multiple imputation assuming Missing At Random (MAR) for the FAS.

Statistical Analysis Plan
Protocol No. MT-1186-A02

Mitsubishi Tanabe Pharma America, Inc.

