9.2.1.4. Key Secondary Analyses

The key secondary endpoints will be inferentially analyzed in the pre-specified order to maintain the overall Type I error.

9.2.1.4.1. %Slow Vital Capacity (%SVC) Change from Baseline to week 48

The first Key secondary endpoint is %SVC change from baseline to week 48. This endpoint analysis will be performed on the FAS. All available %SVC data regardless of use of additional/new AMX0035 treatment (ICE1) drug and all available % SVC data up to early

Statistical Analysis Plan
Protocol No. MT-1186-A02

Mitsubishi Tanabe Pharma America, Inc.

discontinuation (ICE2) will be included.

The changes from baseline to all post-baseline visits until week 48 in %SVC will be estimated using a MMRM using SAS PROC MIXED. The model includes response data from all post-baseline visits with no imputation for missing data. The %SVC at baseline, randomization strata of ALSFRS-R rate of decline score during the screening period (2 levels strata of -1,-2 or -3,-4), Geographical Region (3 levels strata of Europe, America or Asia Pacific), Treatment Group, Visit and Treatment-by-Visit interaction will be included as fixed factors in the model. An unstructured covariance structure will be assumed and the denominator degrees of freedom will be computed using the Kenward-Roger method. In case the model will not converge with the unstructured covariance structure, the heterogeneous compound symmetry and the heterogeneous Toeplitz structure will be used instead (in that order). The least-squares mean (LSMEANS) estimates for the mean change from baseline to weeks 48 as well as the difference of the estimates between oral edaravone 105 mg daily versus oral edaravone 105 mg on/off regimen will be displayed with their corresponding standard errors, p-values, and 95% CI.

9.2.1.4.2. ALSAQ40 Change from Baseline to week 48

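### The subgroup MMRM in SAP 9.4 leaves out subgroup-by-visit, so its three-way interaction p-value mixes differing prognosis with effect modification

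*SAP*

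**What the plan says.** SAP 9.4 covers subgroup analyses of the key and other secondary endpoints. For change in %SVC, ALSAQ-40 and ALSFRS-R it takes an MMRM and adds an "additional fixed factor for the subgroup variable, the subgroup by treatment interaction as well as the subgroup by treatment by visit interaction". It then states: "The influence of each subgroup factor will be investigated using the p-values for the interaction terms". The three-way p-value is therefore one of the statistics by which a factor is assessed.

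The MMRM being extended is written out in SAP 9.2.1.4.1: "Treatment Group, Visit and Treatment-by-Visit interaction will be included as fixed factors in the model". The endpoint's baseline value, the decline stratum and region also enter, each without a visit interaction. On covariance it says "An unstructured covariance structure will be assumed". Neither section lists subgroup-by-visit.

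For the base model, 9.4 cites section 9.2.1.1. The legible text there says "the primary analysis will be the CAFS analysis at week 48 using ANCOVA following multiple imputation". That is a single-time-point rank analysis, not a repeated-measures model.

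The subgroup list includes the randomization decline stratum (-1, -2 against -3, -4), site of onset, baseline ALSFRS-R, %FVC and %SVC.

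**The concern.** A three-way interaction isolates effect modification over time only if all the two-way terms beneath it are in the model. Here treatment-by-visit and subgroup-by-treatment are present and subgroup-by-visit is not. The three-way term then has to carry any difference in time course between the subgroups, including one that is identical in both arms. Nothing else in the model can take it up, because baseline, stratum and region have no visit interactions.

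This matters most for factors related to speed of progression. The decline stratum is the clearest case, because it is defined by the rate of decline during screening. A significant result there could be read as the daily regimen working differently in fast progressors, when the data show only that fast progressors progress faster.

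**Working it through.** **Anchor on the plan's own figure.** SAP 4.2 gives a difference of 2.6, SD 7, 190 per arm, 30% dropout and two-sided 5%. Completers per arm are 190 × 0.70 = 133. A two-sample t-test gives 85.5% power, as stated (85.7% by normal approximation). The SD of 7 and the range of 133 to 190 per arm are used below. The SAP gives no operating characteristic for the subgroup test.

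**Step 1: what the three-way test contains.** ALSFRS-R and %SVC have six post-baseline visits (Weeks 4, 8, 12, 24, 36, 48). With two arms and a two-level subgroup there are 2 × 2 × 6 = 24 cell means.

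- Terms before the three-way: intercept 1 + treatment 1 + visit 5 + treatment-by-visit 5 + subgroup 1 + subgroup-by-treatment 1 = 14.
- Adding the three-way term as listed saturates the model at 24, so the test has 24 − 14 = 10 df.
- With subgroup-by-visit (5 df) entered first, the rank is 19 and the three-way test has 24 − 19 = 5 df.

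Half of the 10 df are therefore subgroup-by-visit. For ALSAQ-40 (Weeks 24 and 48) the ranks are 6 and 8, giving 2 df. With subgroup-by-visit present the rank before the three-way term is 7, leaving 1 df.

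**Step 2: false rejection with no effect modification.** Assume the subgroups differ by *d* points at Week 48, growing linearly and equally in both arms. Let **t** = (4, 8, 12, 24, 36, 48)/48. Assume a random slope plus error SD 2: Σ = 45**tt**′ + 4I, so the Week 48 variance is 45 + 4 = 49 = 7².

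The noncentrality is λ = N·p(1−p)·κ·d², where κ = **t**′Σ⁻¹**t** − (**t**′Σ⁻¹**1**)²/(**1**′Σ⁻¹**1**). The subtracted part is what the subgroup main effect removes.

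- **t**′**t** = 1.9097, **1**′**t** = 2.75 and 4 + 45 × 1.9097 = 89.94.
- **t**′Σ⁻¹**t** = 1.9097/89.94 = 0.02123.
- **t**′Σ⁻¹**1** = 2.75/89.94 = 0.03058.
- **1**′Σ⁻¹**1** = (6 − 45 × 2.75²/89.94)/4 = 0.5540.
- κ = 0.02123 − 0.03058²/0.5540 = 0.01955.

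For equal subgroups (p = 0.5), λ = 1.30d² at 133 per arm (N = 266) and 1.86d² at 190 per arm (N = 380). The 5% critical value of chi-square on 10 df is 18.31.

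| d at Week 48 | λ, 133 per arm | λ, 190 per arm | Closed form | Simulation |
|---|---|---|---|---|
| 1 | 1.30 | 1.86 | 9–12% | about 10% |
| 2 | 5.20 | 7.43 | 28–40% | 30–42% |
| 3 | 11.70 | 16.71 | 63–81% | 64–83% |
| 4 | 20.80 | 29.71 | 90–98% | 91–99% |

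With an 80/20 split the rates are 18–26% at 2 points and 41–59% at 3.

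**Step 3: robustness.** A further simulation used 380 patients, 30% random dropout, a true effect of 2.6 in both subgroups, and either a random-slope or a Brownian covariance (1,500 runs per scenario). Rejection by the listed three-way test was 4.5% at no difference, 9–11% at 1 point, 52–60% at 2.6, 93–97% at 4 and about 100% at 6. With only two visits it was 50–62% at 2.6 points (2.6/7 = 0.37 SD). With subgroup-by-visit added, the three-way test stayed at 4.8–5.2% throughout. The visit-averaged subgroup-by-treatment test and the Week 48 contrast stayed at about 4–6%.

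**Step 4: scale for the decline stratum (an assumption).** The stratum midpoints are −1.5 and −3.5, a gap of 2 points per 8 weeks. Full persistence over 48 weeks would give 2 × 6 = 12 points, so a 3-point gap needs 3/12 = 25% of it to persist.

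**The case against.** The strongest reply is that little depends on this p-value. The rank is 24 with or without subgroup-by-visit, so fitted means, subgroup treatment effects, their intervals and the ALSFRS-R forest plot are identical. The subgroup-by-treatment p-value is reported alongside and keeps its level. The analyses concern secondary endpoints, the SAP speaks of investigating influence rather than deciding on it, and subgroup tests are outside the fixed sequence in SAP 7.3. All of this stands.

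It also stands that the documents give no between-subgroup difference in decline, no reason for choosing the listed factors, and no SD for %SVC or ALSAQ-40. The covariance is assumed too. The subgroup code is not visible and the SAP does not state the test type (SAS Type 3 is assumed here), so a programmer may intend the full hierarchy. The written list, however, says otherwise.

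On the cross-reference, text may be missing from 9.2.1.1. Protocol 17.4.5.1 keeps an MMRM alongside CAFS, so it cannot be said that 9.2.1.1 contains no MMRM. What is legible there is the CAFS ANCOVA.

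A reader might infer that any subgroup declining faster in both arms will be flagged as an effect modifier. The figures do not support that: the rate is about 10% at 1 point and near certain only from about 4 to 6 points in equal subgroups. Nor is it supported that subgroup estimates are biased or that family-wise error is inflated.

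**Conclusion.** The point holds for one statistic. As listed in SAP 9.4, half the degrees of freedom of the three-way test concern prognosis and not effect modification, so its p-value does not answer the question it is used for. That part is algebra and needs no assumption beyond reading the list of terms as complete.

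The size is conditional. It rests on the plan's SD of 7, an assumed covariance and an assumed difference in decline common to both arms. Across 1 to 4 points at Week 48 in equal subgroups, the false rejection rate runs from about 10% to 90–99%, and it is lower in unequal subgroups. The decline stratum is the most exposed factor because of how it is defined. This should be corrected, but no primary or confirmatory conclusion depends on it.

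**What to change.** In SAP 9.4:

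1. Add subgroup-by-visit to the listed terms.
2. Name the Week 48 subgroup-by-treatment contrast (1 df for a two-level factor) as the interaction test to report. It can be estimated from the same model. The subgroup-by-treatment p-value averages over all visits, so it does not test Week 48 specifically.
3. Cite 9.2.1.4.1 as the base MMRM instead of 9.2.1.1.

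The cost is SAP wording and one model term. No model degrees of freedom are lost and the fitted means do not change. The three-way test goes from 10 to 5 df (2 to 1 for ALSAQ-40) and then tests only whether the treatment effect over time differs by subgroup.
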